8.3 Treatment Period

During the Treatment Period, which occurs over a duration of 9 to 15 weeks (Visits 5 to 18), participants will complete three treatments. Each treatment consists of an Experimental Session, followed the morning after by an Integrative Session, phone follow-ups over the next week, a second Integrative Session within 2 weeks, and a third Integrative Session within 3 to 5 weeks. The Experimental Sessions will be scheduled 3 to 5 weeks apart. The CAPS-5 will be assessed at two time points during the Treatment Period: CAPS-5 T2 after Integrative Session 1.2 (Visit 7) and CAPS-5 T3 after Integrative Session 2.2 (Visit 12). The Primary Outcome CAPS-5 T4 will be assessed after the last Experimental Session during the Follow-up Period.

8.3.1 Experimental Sessions

There will be three open-label Experimental Sessions (Visits 5, 10, 15). Procedures for MDMA-assisted psychotherapy will remain the same across all sessions and all procedures regardless of

dose received. Experimental Sessions must be at least 8 hours long, measured from 30 minutes prior to IP administration.

Experimental Session 1 (Visit 5) will occur within 1 week of the Baseline CAPS-5 (Visit 3) assessment. If the Baseline CAPS-5 assessment is completed outside of the allowed window, the investigator should consult the CRA and Medical Monitor to determine if the assessment should be repeated. The first Experimental Session will include 80 mg of IP followed by a supplemental half-dose 1.5 to 2 hours after the initial dose unless contraindicated.

MP16 Protocol

- Experimental Session 2 (Visit 10) will occur within 3 to 5 weeks of Experimental Session 1 (Visit 5) and after Integrative Session 1.3. A dose of 80 or 120 mg MDMA will be administered. A supplemental half-dose will be administered 1.5 to 2 hours after the initial dose unless contraindicated.
- Experimental Session 3 (Visit 15) will occur within 3 to 5 weeks of the second Experimental Session (Visit 10) and after Integrative Session 2.3. A dose of 80 or 120 mg MDMA will be administered. A supplemental half-dose will be administered 1.5 to 2 hours after the initial dose unless contraindicated.

Table 7: Schedule of	f Procedures	s for Experimenta	l Sessions
----------------------	--------------	-------------------	-------------------

Approximate Time	Procedure or Action
9:30	Urine drug screen and pregnancy test, concomitant medication
	information collected, participant acclimated to environment, C-SSRS
9:55	Baseline BP, body temperature, pulse
10:00	IP Administration, Begin video recording
11:30	BP, body temperature pulse
	Supplemental Dose Administration, unless contraindicated
17:30	C-SSRS, BP, body temperature, pulse

Pre-IP administration

- On the day of the Experimental Session, the participant will arrive approximately 30 to 60 minutes prior to IP administration.
- The site team will ensure the participant has not used caffeine or nicotine 2 hours prior, and fasted for 10 hours prior to IP administration and complied with all other requirements per Section 4.3 Lifestyle Modifications.
- The site team will inquire about any possible changes in health to ensure the participant continues to meet all eligibility requirements and record AEs as described in Section 11.0
- The site team will instruct the participant that they will not be able to use caffeine or nicotine at least 6 hours after the IP administration.
- The site team will complete urine drug screen, pregnancy test, and concomitant medication review.
 - a. A positive drug screen will be reviewed by the site physician and may be cause for delaying IP administration to a later time, rescheduling the session to a later date, or withdrawing the participant from the study, based on Medical Monitor review.
 - b. A positive pregnancy screen is cause for withdrawal from the protocol.
- The therapy team will administer Since Last Visit C-SSRS.
- The therapy team will review procedures for the Experimental Session with the participant and discuss the participant's goals, intentions, and concerns and some of the commonly experienced effects of MDMA. The choice of whether to keep the dose the same or change it from the first Experimental Session will be made by the therapy team

in consultation with the site physician based on observed response, tolerability to the previously administered dose, and discussion with the participant.

- If the participant continues to be eligible, the session will proceed.
- Baseline blood pressure, body temperature, and pulse will be measured just prior to administration of the initial dose.

During the Experimental Session

- After video recording has begun, at approximately 10:00 in the morning, a qualified staff
 member will administer the initial dose of IP with an electrolyte-containing fluid. The
 participant will sit or recline on comfortable furnishings. Eyeshades and a program of
 music will be provided for the participant if they wish to use them. Whenever they wish,
 participants may speak to the therapy team, who will provide guidance and support, as
 needed.
- After the first hour, if the participant has not spoken spontaneously, the therapy team will
 check in with them about the nature of the experience. For the rest of the experience, as
 appropriate, the therapy team will support and encourage the participant in emotional
 processing and resolution of whatever psychological material is emerging, as described in
 the Treatment Manual.
- Electrolyte-containing fluids will be provided throughout the session but not to exceed three liters overall.
- Blood pressure, body temperature, and pulse will be measured approximately 1.5 to 2 hours after the initial dose, before the supplemental dose is administered.
- The site physician will be contacted with a brief description of how the session is progressing and the recent vital signs. The site physician will approve or deny the administration of the supplemental dose. If medical attention is needed, the site physician will provide further instruction or consult the Medical Monitor.
- A supplemental half-dose will be administered with a glass of electrolyte-containing fluid approximately 1.5 to 2 hours after the initial dose, unless contraindicated.
- Food will be provided during the latter part of the session.
- If there is an approved companion, that person may arrive as agreed upon but will wait in the waiting room until a member of the therapy team brings them to the session room. Alternatively, the companion may arrive after the session has ended.

End of Experimental Session

- The therapy team will administer Since Last Visit C-SSRS.
- The therapy team will record AEs and concomitant medications.
- The session may be ended if all medical and psychiatric parameters are acceptable, elevations in vital signs have resolved to pre-IP levels, the participant is alert, ambulatory, and emotionally stable, and the night attendant has arrived.
- The therapy team or site physician shall remain available to participants via 24-hour cellular phone for integration, as needed.

Overnight Stay (See Appendix A for sub-study with exceptions)

- Participants will remain overnight in an appropriately furnished room at or near the study site until after the Integrative Session the morning after each Experimental Session. With prior approval of the therapy team, a companion may accompany the participant during the overnight stay.
- An attendant will check in periodically on the participant during the overnight stay, even if a companion is present. The attendant will monitor participant condition and will help participants relax during the overnight stay. The attendant will be an individual with some previous training in managing psychological distress and will be supportive but not

- intrusive. If there is an emergency or the participant needs additional support, the attendant can contact the therapy team.
- The participant and a companion (if applicable) will receive information that will allow them to contact the therapy team during the overnight stay in the case of an emergency or to request for additional support.
- Participants will be encouraged to use much of the time during their overnight stay for rest and as a period of reflection and integration in a quiet atmosphere.
- The participant will be driven home after the integration session by either a driver arranged by the participant, by site personnel or taxi.

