5.3.4 Early Termination from the Study

Participants who are removed from the study after they are enrolled and receive IP but do not complete the study may fall into one of these categories: Post-Dosing Early Termination or Dropout. If the participant has received IP in at least one Experimental Session and completed one CAPS-5 assessment beyond Baseline, they will be considered evaluable. All participants who receive IP in at least one Experimental Session will be included in all safety analyses.

Participants can withdraw from treatment or withdraw consent at any time for any reason without judgment. The site team can withdraw a participant if, in their clinical judgment, it is in the best interest of the participant or if the participant cannot comply with elements of the protocol that are critical for safety or for the scientific integrity of the study. If the site team makes the decision to terminate the participant from treatment or the study, they will explain the reason for withdrawal and document in the participant's source records and eCRF. If a participant develops any Exclusion Criteria that, in the opinion of the Medical Monitor or Site, affects the safety of the participant, including psychiatric diagnosis, pregnancy, or requiring use of prohibited medications, the participant will discontinue treatment in Experimental Sessions but remain in the study for the associated Integrative Sessions. Any time a participant terminates from the study early, the site team will attempt to obtain information about AE outcomes if appropriate, as determined by the site physician and Medical Monitor. The site team will provide the participant with an Exit Plan as described in Section 8.4.3.2 Exit Plan.

 Post-Dosing Early Termination: Participants who discontinue study treatment but continue to participate in study evaluations and outcome assessments. Data collection by IRs will continue on the same schedule as planned through Study Termination visit procedures.

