11.3.3 Follow-up Requirements

Details of all pregnancies in study participants will be collected after Enrollment (Visit 0) and collected through 10 days after the last Experimental Session. Pregnancies should be reported to the sponsor via telephone or email within 24 hours of site staff awareness.

In the event of a pregnancy, the participant will discontinue Experimental Sessions but may continue with non-drug Integrative Sessions, the next CAPS-5 assessment, and Study Termination procedures. At a minimum, prior to withdrawal from the study, efforts should be made to assess the final CAPS-5 immediately and complete Study Termination procedures.

The investigator will collect follow-up information on the participant and neonate and forward to the sponsor until the outcome of the pregnancy, which will be reported on an optional Pregnancy eCRF. Any termination, elective or spontaneous, will be reported. Abnormal pregnancy outcomes, such as spontaneous abortion, fetal death, stillbirth, congenital abnormalities, or ectopic pregnancy, will be reported as SAEs.

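### The protocol gives conflicting exits for a dosed participant with a positive pregnancy screen: 8.3.1 reads as leaving the study, 5.3.4 keeps her in it, and 11.3.3, 8.4.2 and 8.4.3 do not match 5.3.4

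*Protocol*

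**What the plan says.** Protocol 8.3.1, in the checks before each dose, states: "A positive pregnancy screen is cause for withdrawal from the protocol". It attaches no follow-up instruction and no cross-reference.

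Protocol 5.3.4 covers a participant who develops an exclusion criterion that, "in the opinion of the Medical Monitor or Site, affects the safety of the participant, including psychiatric diagnosis, pregnancy" being among the examples. In that case "the participant will discontinue treatment in Experimental Sessions but remain in the study for the associated Integrative Sessions". For Post-Dosing Early Terminations, defined there as people who stop treatment but carry on with evaluations, "Data collection by IRs will continue on the same schedule as planned through Study Termination visit procedures".

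Protocol 11.3.3, the pregnancy section, says "the participant will discontinue Experimental Sessions but may continue with non-drug Integrative Sessions, the next CAPS-5 assessment, and Study Termination procedures". It then sets a floor: "At a minimum, prior to withdrawal from the study, efforts should be made to assess the final CAPS-5 immediately and complete Study Termination procedures".

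Protocol 8.4.2 has anyone withdrawn from treatment complete a final CAPS-5 at once. Protocol 8.4.3 has those withdrawn from treatment who continued in follow-up complete the Study Termination visit at once. It adds that, once those measures are done, the participant counts as terminated from the study.

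Protocol 9.4 commits the sponsor to complete data collection, including for participants who discontinue treatment. SAP 8.7.1 leaves CAPS-5 data collected after treatment discontinuation out of the primary de jure analysis. SAP 8.2 includes them in the supportive de facto analysis.

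**The concern.** The staff who read a positive test on a session day are working from 8.3.1. Read plainly, that bullet ends participation in the study. Section 5.3.4 tells them to stop dosing and keep the participant. Section 11.3.3 agrees with 5.3.4 on stopping dosing, but it makes staying optional and does not carry the CAPS-5 schedule through to V19. Sections 8.4.2 and 8.4.3 then send the participant to closing assessments immediately, even if she is staying. No rule of precedence is given.

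At stake are the planned CAPS-5 assessments of a dosed participant who has not withdrawn consent, the consistency of her disposition category across sites, and the scheduled C-SSRS and adverse-event collection in someone exposed to MDMA who is pregnant. Data that 9.4 promises and the de facto analysis is meant to use could be missing only because of which section a site followed.

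**Working it through.** The plan has no figure of its own to reproduce here. The check sets the sections side by side and then adds visit windows.

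**1. Where the conflict applies.** Protocol Table 5 places pregnancy screens at Screening, V4, V5, V10 and V15. The V5 screen precedes any dose. Only a positive at V10 or V15 concerns a dosed participant.

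**2. The sections side by side, for a dosed participant.**

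| Protocol section | Applies to | Stays in the study? | CAPS-5 afterwards |
|---|---|---|---|
| 8.3.1(b) | positive pregnancy screen | no, on the plain reading | none stated |
| 5.3.4 | pregnancy judged to affect safety | yes | planned schedule, if evaluations continue |
| 11.3.3 | pregnancy | optional | the next one; immediate one, by efforts, before leaving |
| 8.4.2 | any withdrawal from treatment | not stated | immediate final one |
| 8.4.3 | withdrawal from treatment, including those in follow-up | ends after the termination visit | none stated |

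**3. Planned CAPS-5 assessments still to come.** After V10 these are V13 and V19; after V15, only V19.

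- 5.3.4: V13 and V19 for a V10 positive; V19 for a V15 positive. This joins two statements, because the pregnancy sentence mentions only Integrative Sessions and the rater schedule sits under Post-Dosing Early Termination.
- 11.3.3: the next assessment is V13 for a V10 positive and V19 for a V15 positive. It therefore differs from 5.3.4 by at most V19, and only for a V10 positive.
- Plain 8.3.1(b): neither planned assessment is secured. An immediate CAPS-5 may be done through 8.4.2 or 11.3.3.

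**4. How early an immediate CAPS-5 would be.** Inputs, in weeks after Baseline (V3): V5 at 0–1 (8.3.1); sessions 3–5 weeks apart (8.3); V19 at 15–21 and 6–10 weeks after V15 (8.4.2).

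- V10 = V5 + 3 to 5 = 3–6.
- V15 = V10 + 3 to 5 = 6–11.
- V10 to V19 = (3 to 5) + (6 to 10) = **9–15 weeks**. Both ends fit the Baseline window: V10 at 6, V15 at 9, V19 at 15; and V10 at 6, V15 at 11, V19 at 21.
- V15 to V19 = **6–10 weeks**.
- V20 is 1 to 9 days after V19. V10 to V20 is then 9 weeks + 1 day to 15 weeks + 9 days, about 9–16 weeks. V15 to V20 is 6 weeks + 1 day to 10 weeks + 9 days, about 6–11 weeks. An immediate termination visit would end scheduled C-SSRS and adverse-event collection that much early.

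These gaps assume V19 keeps its place in the full schedule although the remaining sessions are not given. Tied to Baseline alone, the V10 gap is 15 − 6 = 9 to 21 − 3 = 18 weeks, and the V15 gap is 15 − 11 = 4 to 21 − 6 = 15 weeks.

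**5. Which analyses use the data.** A participant on schedule has had the V8 CAPS-5 before V10, so she is already in the mITT set. Everything after the positive screen is after treatment discontinuation. SAP 8.7.1 excludes it from the primary analysis; SAP 8.2 includes it in the de facto analysis.

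**The case against.** The best reply is that *protocol* in 8.3.1(b) may not mean the study. Section 10.2.2.2 has a hospitalised participant suspended from the protocol until recovery, which fits a pause in treatment. The neighbouring bullet on drug screens speaks of the study, so the change of word could be deliberate. Being cause for withdrawal need not mean automatic withdrawal. Section 10.2.3.4 also sends readers to 11.3 for pregnancy.

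This stands in part: a treatment-only reading is possible. But 4.1 uses the same word for enrolling in the study, and 10.1.2 and 12.3 mention follow-up expressly when only treatment ends. Turning to 11.3.3 does not settle matters either, since it differs from 5.3.4.

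A second reply is that assessment counts rest on readings the text does not fix. Section 8.4.2 says treatment withdrawals *also* complete an immediate CAPS-5, which may mean in addition to the planned ones. The withdrawal in 8.4.3 may mean a later withdrawal from follow-up. This stands: a reader might infer that a definite number of planned assessments is replaced, and the documents do not establish that. Loss or replacement is a possibility that depends on the section followed.

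A reader might also infer that safety follow-up is abandoned. It is not. Under 5.3.4, "Any time a participant terminates from the study early, the site team will attempt to obtain information about AE outcomes if appropriate". Under 11.3.3, "The investigator will collect follow-up information on the participant and neonate and forward to the sponsor until the outcome of the pregnancy". What could end early is the scheduled collection.

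**Conclusion.** The inconsistency is real and minor. For a V10 or V15 positive, a plain reading of 8.3.1(b) ends study participation while 5.3.4 continues it, and 11.3.3 matches neither fully. The mismatch of 8.4.2 and 8.4.3 with the planned schedule in 5.3.4 is a separate fault that reaches every treatment discontinuation, not only pregnancy.

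The possible cost is V13 and/or V19 lost or replaced by a CAPS-5 about 9–15 weeks (V10) or 6–10 weeks (V15) before V19, with scheduled C-SSRS and adverse-event collection cut short. This rests on the plain reading of *protocol*, on taking the two statements in 5.3.4 together, and on V19 keeping its place in the full schedule.

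A reader might infer bias in the primary result. The documents do not support that, because the de jure analysis excludes these assessments whichever exit is used. The effect falls on the supportive de facto analysis, the disposition table and scheduled safety follow-up. Few participants are likely to be affected. The documents give no pregnancy rate, and their all-cause dropout and early-termination figures cannot stand in for one.

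**What to change.** Make these wording changes in one amendment.

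1. **8.3.1(b):** replace withdrawal from the protocol with *discontinuation of Experimental Sessions; participants who have received IP remain in the study under 5.3.4 and 11.3.3 unless they withdraw consent*.
2. **11.3.3:** replace the permissive wording and the single next CAPS-5 with *will be asked to continue with Integrative Sessions, the remaining planned CAPS-5 assessments and Study Termination procedures*. Keep the immediate CAPS-5 for those leaving the study.
3. **8.4.2 and 8.4.3:** state that the immediate final CAPS-5 and termination visit apply to participants leaving the study, and that those who stop treatment but stay keep the planned V19 and V20.

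Section 5.3.4 needs no change. A V5 positive should not be labelled a Pre-Dosing Early Termination unless 5.3.3 and SAP 1.0 are also amended: 5.3.3 ties that label to enrollment not being confirmed at V4, and SAP 1.0 places it in the Preparatory Period. Neither covers someone confirmed at V4 but never dosed.

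The cost is one bullet, one phrase and one sentence each in 8.4.2 and 8.4.3, with no new visits or procedures. Dosing still stops for pregnancy. Change 3 applies to all treatment discontinuations. If 8.4.2 intended an additional assessment, those who stay would lose that extra early CAPS-5, which is a small price for one consistent schedule.

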8.3.2 Telephone Contact After Experimental Sessions

The goal of the telephone contact is to assess health changes, ensure participant safety, and offer support. The therapy team will follow-up with the participant by telephone on the second and seventh day after each Experimental Session, with two additional telephone contacts in between. Each call will last on average five to 15 minutes but could be longer to address participant concerns and to adequately assess wellbeing. Additional telephone contact can be initiated at the request of the therapy team or participant.

At each telephone contact, the therapy team will:

- Inquire about any possible changes in health, assess the participant's mental health and
 the status of any previously recorded AEs, and record AEs as described in Section 11.0
 Safety
- Inquire about concomitant medication use and adherence
- Offer support in accordance with the Treatment Manual
- On the second and seventh contact day after an Experimental Session the therapy team will administer the Since Last Visit C-SSRS.

8.3.3 Integrative Sessions

After each Experimental Session, three Integrative Sessions will take place. Each session will consist of 90 minutes of psychotherapy.

Treatment 1

- Integrative Session 1.1 (Visit 6): morning after Experimental Session 1 (Visit 5)
- Integrative Session 1.2 (Visit 7): approximately 2 weeks after Experimental Session 1 (Visit 5)
- Integrative Session 1.3 (Visit 9): within 3 to 5 weeks of Experimental Session 1 (Visit 5) and 1 to 7 days in advance of Experimental Session 2 (Visit 10). This visit serves two purposes: to continue integration and to prepare for the next Experimental Session. The participant will complete the LEC-5 and PCL-5 self-report measures.

Treatment 2

- Integrative Session 2.1 (Visit 11): morning after Experimental Session 2 (Visit 10)
- Integrative Session 2.2 (Visit 12): approximately 2 weeks after Experimental Session 2 (Visit 10)
- Integrative Session 2.3 (Visit 14): within 3 to 5 weeks of Experimental Session 2 (Visit 10) and 1 to 7 days in advance of Experimental Session 3 (Visit 15). This visit serves two purposes: to continue integration and to prepare for the next Experimental Session. The participant will complete the LEC-5 and PCL-5 self-report measures.

Treatment 3

- Integrative Session 3.1 (Visit 16): morning after Experimental Session 3 (Visit 15)
- Integrative Session 3.2 (Visit 17): approximately 2 weeks after Experimental Session 3 (Visit 15)
- Integrative Session 3.3 (Visit 18): within 3 to 5 weeks after Experimental Session 3 (Visit 15). This visit will be the final Integrative Session prior to entering the follow-up period. The participant will complete the LEC-5 self-report measure.

During Integrative Sessions, the therapy team will:

- Record the session.
- Inquire about any possible changes in health. Assess the participant's mental health and the status of any previously recorded AEs. Record AEs as described in Section 11.0 Safety.
- Inquire about concomitant medication use and adherence.
- Administer Since Last Visit C-SSRS to determine suicidal risk.
- Discuss and review events that occurred with the participant during the Experimental Session, including thoughts, feelings, and memories. If necessary, the therapy team will help the participant to reduce any residual psychological distress they are experiencing. The therapy teams will also encourage the transfer of states of acceptance, feelings of intimacy, closeness, and reduced fear experienced in Experimental Sessions to emotionally threatening everyday situations. The therapy teams will be supportive, validate the experience, and facilitate understanding and emotional clearing.
- Be accessible for additional support via phone or telemedicine if needed.
- At each third Integrative Session, direct the participants to complete the LEC-5.
- At each third Integrative Session, direct the participants to complete the PCL-5 with the exception of Visit 18.

